5. ANALYSIS AND REPORTING

All final, planned analyses will be performed after the last patient has completed the last study visit and end-of-study assessments and all relevant study data have been processed and integrated into the analysis data base. Any post-hoc, exploratory analyses completed to support planned study analyses, but which were not identified in this SAP, will be documented and reported in appendices to the CSR. Any results from these unplanned analyses (post-hoc) will also be clearly identified as such in the text of the CSR.

6. SAMPLE SIZE DETERMINATION

The study is planned to enroll approximately 470 patients total in a 1:1 randomization, that is, 235 patients in each of the TNX-102 SL and placebo arms. Using a two-sided t-test with an alpha level of 0.05, a sample size of 235 per group provides a power of approximately 90% if the effect size is 0.3.

7. ANALYSIS POPULATIONS

In the case that the study goes to full enrollment or has a sample size increase, the following analysis populations are planned for this study:

- All Patients: used for summaries of dispositions of patients; tabulations of dispositions may also use the populations below.
- Safety population: all patients who receive at least one dose of the investigational product. All safety analyses will be performed using this population, analyzed as treated.
- Intention-to-treat (ITT) population: all patients who are randomized and have at least one post-baseline daily diary entry. This is the primary population for efficacy analyses, and patients will be analyzed based on their randomized treatment.

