13.1. Populations for Analysis

In the case that the study goes to full enrollment or has a sample size increase, the following analysis populations are planned for this study:

- All Patients: used for summaries of dispositions of patients; tabulations of dispositions may also use the populations below.
- Safety population: all patients who receive at least one dose of the investigational product. All safety analyses will be performed using this population, analyzed as treated.
- Intention-to-treat (ITT) population: all patients who are randomized. This is the primary population for efficacy analyses, and patients will be analyzed based on their randomized treatment.

In the case of an early stop for efficacy or for futility from the interim analysis, the following populations will be utilized:

- All Patients: used for summaries of dispositions of patients; tabulations of dispositions may also use the populations below.
- Interim Safety population: all patients who receive at least one dose of the investigational product and included in the cohort of interim analysis patients. All safety analyses will be performed using this population, analyzed as treated.
- Interim ITT population: all patients who are randomized and included in the cohort of interim analysis patients. This is the primary population for efficacy analyses, and patients will be analyzed based on their randomized treatment.
- Full Safety population: all patients who receive at least one dose of the investigational product. This will be used for supportive safety analyses on all patients exposed in the study, analyzed as treated.

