13.4. Efficacy Analyses

13.4.1. Primary Efficacy Analysis

The primary efficacy parameter will be the contrast between TNX-102 SL and placebo in the weekly mean change in worst pain score from Baseline to Week 14. The weekly pain score will be based on the weekly average of the daily diary patient self-reported 24-hour recall worst Long COVID pain intensity scores using an 11-point (0–10) NRS. A weekly value will be calculated as long as at least one daily measure is recorded.

The primary ITT analysis will provide the following causal estimand for the primary analysis: the difference in the weekly mean change from Baseline of the daily patient self-reported 24-hour recall worst Long COVID pain intensity rating using an 11-point (0–10) NRS evaluated at the Week 14 endpoint in all randomized patients attributable to the initially randomized treatment assignment.

The primary analysis will use a Mixed Model Repeated Measures (MMRM) approach with multiple imputation (MI) for missing data. Covariates in the model will include the fixed categorical effects of treatment, pooled site (with small sites pooled into a single large site), study week, and treatment by study week interaction, as well as the continuous fixed covariates of baseline score and baseline score by study week interaction. An unstructured covariance structure will be used to model the within-patient errors. If this analysis fails to converge, the following structures will be tested in this order: first order ante dependence, heterogeneous first order autoregressive, heterogeneous compound symmetry, and compound symmetry with the first to give convergence used. The Kenward-Roger approximation will be used to estimate the denominator degrees of freedom (DDFM) with the unstructured matrix; other covariance structures will utilize the sandwich matrix and the Statistical Analysis System (SAS) default DDFM. The least square (LS) means and differences across the 20 MI repeats will be combined using SAS procedure MIANALYZE (Rubin, 1976). Significance testing will be based on least-squares means and two-sided 95% confidence intervals will be presented. The p-values will be compared against a two-sided alpha of 0.046.

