8. GENERAL ISSUES FOR STATISTICAL ANALYSIS

8.1 General Statistical Methodology

Descriptive summaries will be provided where appropriate for each of the primary and secondary variables. In general, tables will summarize data by treatment group and visit. All patients for a population in each treatment group will be grouped together; patients that reduce dose from two tablets per day to one tablet per day will be not be reported separately for the analyses described in this SAP, unless otherwise noted. If there are more than 10 patients in the active arm with a dose reduction at any point in the study, summary statistics on key outcomes may be reported for patients with dose reductions.

Baseline characteristic and safety tables will be completed for the Safety Population unless otherwise specified. Efficacy tables will be presented for the ITT Population.

Continuous, quantitative variable summaries will include the number of patients (N) with non-missing values, mean, standard deviation, median, minimum, and maximum.

Categorical, qualitative variable summaries will include the frequency and percentage of patients who are in the particular category. In general, the denominator for the percentage calculation will be based upon the total number of patients in the study population for the treatment group unless otherwise specified.

Baseline values are defined as the last non-missing measurement prior to the first dose of study drug. For scores obtained via diary, baseline will be defined as the average of the scores from the 7 days prior to the baseline visit. Change from baseline will be defined as the post-baseline visit value minus the baseline value.

For continuous endpoints where treatment groups are compared via linear models with the difference in LS means, the effect size will be calculated and included as a summary statistic using the difference in LS means and its standard error, transformed to a standard deviation.

Study day is defined as assessment date – first dose date +1 for dates after the first dose date and assessment date – first dose date for dates prior to the first dose.

All analyses will be performed using SAS® Software version 9.4 or later.

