10.2 Secondary and Exploratory Efficacy Analyses

Secondary efficacy analyses will be based on the ITT population only.

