10.2.3 Categorical Endpoints

A categorical analysis of PGI-C will compare the treatment arms with a difference in proportions Z test (equivalent to a Pearson's Chi Squared). Patients with results of "very much improved" or "much improved" (defined as responders) will be compared to all other categories (defined as non-responders). Patients with missing data will be considered non-responders. The percentages of responders and the 95% CIs of the percentages as well as the difference in the percentages and its 95% CI will be reported. In the case of sparse data (<5 patients expected in a cell), Fisher's exact test will be employed. A summary of frequency counts for all PGI-C responses for each time point will be presented; Week 14 is of primary interest and all other time points are considered exploratory.

Exploratory analyses of the following endpoints will use identical methodology as the PGI-C analysis:

- Proportion of patients with a $\geq 30\%$ improvement from Baseline to Weeks 1–14 in the daily self-reported worst Long COVID pain intensity score
- Proportion of patients with a $\geq 50\%$ improvement from Baseline to Weeks 1–14 in the daily self-reported worst Long COVID pain intensity scores

The number and percentage of patients in each PCFS category will be reported at each visit where it is collected.

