13. CHANGES FROM PLANNED ANALYSIS

Consequently, a number of analyses were simplified or removed from the SAP that were planned in the protocol.

- The interim analysis was removed, and the required alpha spend eliminated.
- The imputation algorithm was removed from the primary analysis and shifted to an optional sensitivity analysis. As such, the ITT population was updated to include the requirement that patients have at least one post-baseline diary entry.
- Lab summaries were eliminated; lab results will be presented in listings
- C-SSRS summaries were simplified
- Site covariate removed due to low patient counts spread over many sites

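### The SAP's diary-entry condition for ITT is justified only for the diary models but governs all efficacy endpoints, so some randomised patients leave the responder denominators instead of counting as non-responders

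*SAP*

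**What the plan says.** Protocol section 13.1 sets the efficacy population as "Intention-to-treat (ITT) population: all patients who are randomized". Protocol section 13.4.1 states the estimand for the effect "in all randomized patients attributable to the initially randomized treatment assignment".

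SAP section 7 changes the set to "all patients who are randomized and have at least one post-baseline daily diary entry". SAP section 13 discloses the change and ties it to moving imputation out of the primary analysis: "As such, the ITT population was updated to include the requirement that patients have at least one post-baseline diary entry".

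The new set then governs all efficacy. SAP section 8.1 says "Efficacy tables will be presented for the ITT Population" and generally takes the population total as the denominator for percentages. SAP section 10.2 says "Secondary efficacy analyses will be based on the ITT population only". No endpoint is given a different population, and no supportive analysis on all randomised patients is planned.

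Two other rules bear on this:

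- SAP section 10.2.3 says of PGI-C "Patients with missing data will be considered non-responders" and uses the same method for 30% and 50% pain response. Sections 8.1.3 and 8.2.6 agree.
- SAP section 8.1.2 assigns early-termination clinic data to the nearest scheduled visit and includes them in the analysis.

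**The concern.** A patient with no post-baseline diary value adds nothing to a diary mixed model without imputation, so for those models the new condition costs nothing. That argument does not carry over to the other endpoints.

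In a responder analysis, such a patient does carry information under the plan's own convention: no data means no response. Once the population definition has removed the patient, the convention cannot apply. Both arms' response rates rise. If exclusion differs by arm, so does the bias. Whether a patient makes a diary entry after randomisation can depend on treatment, for instance through early intolerance, so this is selection on a post-randomisation event.

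For the clinic scales (PROMIS, SDS, ESS, ISI, PCFS and the body-map scores) the issue is narrower. Protocol section 11.6.2 asks early leavers to attend a termination visit at which these are completed. If such a patient has no diary entry, section 8.1.2 says the data are analysed while section 7 leaves the patient out. PROMIS fatigue and cognitive function are key secondary endpoints, so the overlap needs resolving even if it seldom arises.

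The optional multiple-imputation analysis in SAP section 10.1.3 would not reveal the effect. It refits the primary models, and nothing says it restores the excluded patients.

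**Working it through.** **The plan's own figure.** SAP section 6 gives 235 per arm, standardised effect 0.3, two-sided alpha 0.05 and about 90% power. Normal approximation: 0.3 × √(235/2) = 3.252; 3.252 − 1.960 = 1.292; power 90.2%. The noncentral t gives 90.1%. The figure reproduces and is not in dispute. The plan gives no figure for the responder analyses.

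**Who is affected, by endpoint type.**

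| Endpoint | Patient with no post-baseline diary entry: all-randomised set | SAP set | Loss |
|---|---|---|---|
| Diary pain and sleep models | contributes nothing | excluded | none |
| PGI-C; 30%/50% pain response | non-responder if missing | excluded | leaves the denominator |
| Clinic scales, no post-baseline value | contributes nothing | excluded | none |
| Clinic scales, with a clinic or termination value | contributes | excluded | observed data dropped |

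**Size for a responder endpoint.** Inputs: 235 per arm from SAP section 6, and the pooled two-proportion Z test named in SAP section 10.2.3. Response rates and no-diary rates are assumptions, because the documents give neither. Responder counts x are held fixed, because an excluded patient without data would have been a non-responder.

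- Difference: D = x1/n1 − x2/n2
- Test: z = D / √[p(1 − p)(1/n1 + 1/n2)], with p = (x1 + x2)/(n1 + n2)

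The assumed exclusions of 2%, 4%, 5% and 8% are 5, 9, 12 and 19 patients of 235, leaving 230, 226, 223 and 216.

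| No diary entry, active / placebo | Denominators | 94 vs 70 responders: D, p | 89 vs 70 responders: D, p |
|---|---|---|---|
| All randomised | 235 / 235 | 10.2 points, 0.020 | 8.1 points, 0.064 |
| 2% / 2% | 230 / 230 | 10.4, 0.020 | 8.3, 0.063 |
| 5% / 5% | 223 / 223 | 10.8, 0.018 | 8.5, 0.060 |
| 4% / 2% | 226 / 230 | 11.2, 0.013 | 9.0, 0.045 |
| 8% / 2% | 216 / 230 | 13.1, 0.004 | 10.8, 0.018 |

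One cell in full, 89/226 against 70/230: D = 0.3938 − 0.3043 = 0.0895; p = 159/456 = 0.3487; standard error = √(0.2271 × 0.008773) = 0.0446; z = 2.00; two-sided p = 0.045.

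Equal exclusion adds 0.2 to 0.5 points and barely moves the p-value. At 4% against 2% the gain is about 1 point (0.9 in each column, before rounding of the entries), and at 8% against 2% it is 2.7 to 2.9 points.

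SAP section 13 mentions low patient counts across sites, so a smaller trial is worth one line. With an assumed 50 per arm and 20 against 15 responders, 4%/2% exclusion (48 and 49 left) moves D from 10.0 to 11.1 points and p from 0.295 to 0.257.

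**The case against.** The strongest reply is that almost nobody will meet the condition for exclusion.

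- **Diary use is screened.** Randomisation requires pain scores on at least 5 of the 7 preceding days (SAP section 4.2), and Protocol section 12.1.8 provides reminders and site contact for missed entries. Exclusion needs no post-baseline entry at all. This stands, and it is why the number is probably small.
- **A patient who stops after one dose may still be in the set.** The diary is completed in the evening before dosing, and SAP section 8.2.1 lists diary baseline as Days -7 to -1 with Day 1 as its own row. On that reading a Day 1 entry comes after baseline. The general baseline rule in SAP section 8.1, the last value before first dose, points the other way. The SAP does not settle it, so one cannot assert that every one-dose dropout is removed.
- **The non-responder rule is not literally contradicted.** It works within the chosen population and still catches every dropout with one diary entry. That is right; the defect is that the population is chosen too narrowly for the rule to do its full work.
- **The change is disclosed and partly recoverable.** SAP section 9.1 reports the numbers randomised and in each population. All-randomised 30%/50% response rates could be recomputed from arm-level counts. PGI-C rates could be too, if the excluded patients have no PGI-C value. This reduces the harm but leaves the planned analysis as it is.

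A reader might also infer that immediate dropouts in general disappear from the clinic-scale analyses. They do not: a patient with no post-baseline clinic value contributes nothing to those models under any population.

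**Conclusion.** The point holds as a minor one about scope. The diary-entry condition is sound for the diary models and unjustified for the responder endpoints, where it removes patients whom the plan's own convention would count as failures. For clinic scales the loss is confined to patients with a clinic or termination value and no diary entry.

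The size is unknown. It is zero if no such patients occur, 0.2-0.5 points under equal 2-5% exclusion, and about 1 point at 4% against 2%, all under assumed rates. The shift from p = 0.064 to 0.045 needs both a borderline result and an imbalance that no document predicts.

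A reader might infer that the trial's main conclusion is at risk, or that results will be tilted towards active drug. The documents support neither. The primary model is unchanged. PGI-C is a non-key secondary endpoint and the 30%/50% analyses are exploratory, and SAP section 8.1.1.2 treats their p-values as descriptive. Nothing in the documents says that more active than placebo patients will lack a diary entry.

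**What to change.** In SAP sections 7, 8.1 and 10.2:

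- Use all randomised patients, with missing counted as non-response, for PGI-C response and 30%/50% pain response.
- Let any randomised patient with a post-baseline value of the scale enter the PROMIS, SDS, ESS, ISI and PCFS models, consistent with section 8.1.2.
- Rename the diary-entry set modified ITT and use it only for the diary mixed models.
- State whether the Day 1 evening entry counts as post-baseline.

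The cost is SAP wording and one extra population flag. No new data are needed and the primary mixed model does not change. The change should be made before unblinding.

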8. GENERAL ISSUES FOR STATISTICAL ANALYSIS

8.1 General Statistical Methodology

Descriptive summaries will be provided where appropriate for each of the primary and secondary variables. In general, tables will summarize data by treatment group and visit. All patients for a population in each treatment group will be grouped together; patients that reduce dose from two tablets per day to one tablet per day will be not be reported separately for the analyses described in this SAP, unless otherwise noted. If there are more than 10 patients in the active arm with a dose reduction at any point in the study, summary statistics on key outcomes may be reported for patients with dose reductions.

Baseline characteristic and safety tables will be completed for the Safety Population unless otherwise specified. Efficacy tables will be presented for the ITT Population.

Continuous, quantitative variable summaries will include the number of patients (N) with non-missing values, mean, standard deviation, median, minimum, and maximum.

Categorical, qualitative variable summaries will include the frequency and percentage of patients who are in the particular category. In general, the denominator for the percentage calculation will be based upon the total number of patients in the study population for the treatment group unless otherwise specified.

Baseline values are defined as the last non-missing measurement prior to the first dose of study drug. For scores obtained via diary, baseline will be defined as the average of the scores from the 7 days prior to the baseline visit. Change from baseline will be defined as the post-baseline visit value minus the baseline value.

For continuous endpoints where treatment groups are compared via linear models with the difference in LS means, the effect size will be calculated and included as a summary statistic using the difference in LS means and its standard error, transformed to a standard deviation.

Study day is defined as assessment date – first dose date +1 for dates after the first dose date and assessment date – first dose date for dates prior to the first dose.

All analyses will be performed using SAS® Software version 9.4 or later.

8.1.1 Study Success, Adjustments for Multiplicity and Other Alpha Control

8.1.1.1 Study Success

[REDACTED] If the effect size observed for the primary analysis is greater than 0.20, the trial will be considered to have achieved proof of concept and would support further research of the product in this indication.

In the event that statistical significance for the primary is achieved, the multiplicity algorithm below will apply. If statistical significance is not obtained, but proof of concept is declared on the primary, there will be no formal hierarchy or thresholds subsequently considered for secondary endpoints.

8.1.1.2 Multiplicity

To adjust for multiplicity and to control for overall type I error, a sequential test procedure will be applied to the primary and key secondary efficacy endpoints. If the primary analysis produces a result that is statistically significant at the two-sided 0.05 level, a significance level of 0.05 will be used for comparing the key secondary endpoints in an ordered fashion. If the analysis for a key secondary endpoint does not produce a statistically significant result, then the remaining key secondary endpoint analyses will automatically be considered non-significant regardless of the p-value produced.

The order of key secondary endpoints in which they are to be tested is as follows:

- Change from Baseline in the weekly average of the daily diary NRS assessment of sleep quality at the Week 14 endpoint
- Change from Baseline in the PROMIS score for fatigue at the Week 14 endpoint
- Change from Baseline in the PROMIS score for cognitive function at the Week 14 endpoint

No other adjustments for multiplicity will be made and other p-values displayed in the output will be considered for descriptive summary purposes only and will not be used for formal inference. Additional details regarding statistical analysis for the listed endpoints can be found in [Section 10](#).

8.1.2 Data Handling for Patients Who Withdraw/Drop Out from the Study

Patients who withdraw/drop out from the study will have the early termination (ET) data collected at their ET visit included in the analysis at the closest visit (Week 2, 6, 10, 14) where the given data are collected, using midpoints between visits to window the early termination. If this results in two records for a given visit, then the one closest to the targeted date will be used.

[figure not shown]
For example, a patient with valid Week 10 clinic assessment collected on Day 72 that has early termination data collected on Day 79, would have the early termination data mapped to Week 10; however, since Day 72 data is present and closer to the target date, it would be analyzed and the Day 79 data would be excluded. A patient without valid Week 10 data who early terminates on Day 79 would have the Day 79 data analyzed with the Week 10 data.

Patients who provide 14 weeks of diary pain data will be analyzed as completers for purposes of the primary analysis, even if for some reason they are unable to attend a Week 14 final study visit. As a specific example, a patient who successfully provides 14 weeks of diary data as described in [Section 8.2.1](#), but who is unable to attend a final study visit during the required time window because of travel or other circumstances, would be analyzed as a completer for purposes of the primary endpoint, but would be missing non-diary based secondary outcome measures at the Week 14 endpoint. For safety data, the last observation available will be summarized in addition to the presentation above (grouping ET visits with the closest planned visit); this will combine the ET visit data with the completers' Week 14 data, regardless of when the ET occurred.

